3 SYNOPSIS

Title of the clinical investigation

A prospective clinical investigation to assess the diagnostic precision of the artificial intelligence (AI) tool Dermalyzer to identify malignant melanomas in subjects seeking primary care for melanomasuspected *cutaneous* lesions

Investigation code	Investigational Medical Device	IMD classification
AI-DSMM	Dermalyzer	IIb

Intended use

Dermalyzer is a device intended to be used as a decision support system for assessing cutaneous lesions suspected of being melanomas. The input from the device is not intended to be used as the sole source of information for diagnosis. The device should be used in combination with a medical professional assessment of the suspected lesion. Intended to be used by medical professionals. The service does not provide any other diagnosis.

Coordinating/Principal Investigator

[name], assoc.professor, Region Östergötland

Time period for the clinical investigation

Estimated date of first subject enrolled: Q1 2022

Estimated date of last subject completed: Q3 2022

Design of the clinical investigation

This will be a pre-market, prospective, confirmatory, first in clinical setting, pivotal multi-centre, non-interventional clinical investigation to evaluate the clinical safety, performance and benefit of Dermalyzer in patients with cutaneous lesions where malignant melanoma (MM) cannot be ruled out.

Objectives and endpoints

Primary objective

Document	Doc. id.	Version	Page	
Clinical investigation Plan / Investigation code- AI-DSMM/	GR 21- 023	01	9 (52)	_

The primary objective of the investigation is to determine the diagnostic precision of the device; to answer at which level the AI tool Dermalyzer can identify malignant melanomas among cutaneous lesions that are assessed in clinical use due to any degree of malignancy suspicion.

Primary endpoint

The primary endpoint will be measured as the true proportion; by testing if the device based on AI gives correct results as compared with the result of the lesion analysis (the final classification by histopathology (PAD) in at least a certain proportion (π) of the analyses.

Secondary objectives

As secondary objectives a number of analyses will be done.

To evaluate usability and applicability in clinical praxis of Dermalyzer by users (medical professionals)

To gain an increased knowledge and understanding of how digital tools enhanced co-artificial intelligence can assist physicians with the right support for an earlier diagnosis of malignant melanoma.

Secondary endpoints

User questions including System Usability Scale to evaluate the usability and applicability in clinical praxis.

Exploratory objective

To explore health economic aspects of improved diagnosis support

Exploratory endpoints

Collecting health economic related information by survey to participating sites

Number of subjects planned

The estimated number of lesions to be recruited is approximately 500 in order to evaluate 239 eligible lesions, based on power/sample size calculation.

Diagnosis and main eligibility criteria

Inclusion criteria:

Document	Doc. id.	Version	Page	
Clinical investigation Plan / Investigation code- AI-DSMM/	GR 21- 023	01	10 (52)	_

- 1. Patients ≥18 years
- 2. Patients attending a primary care facility with at least 1 suspicious skin lesion where MM cannot be ruled out.
- 3. Willingness and ability to provide informed consent.

Exclusion criteria:

- 1. Cutaneous lesions that are considered as benign by the investigator and thus not subject for further clinical investigation
- 2. Cutaneous lesions in areas that are not suitable for dermoscopy imaging
- 3. Cutaneous lesions in areas with any form of scarring of tissue due to injury
- 4. Damaged or injured non intact skin where the cutaneous lesion is located
- 5. Individuals with skin type V and VI according to the Fitzpatrick scale (darker brown or black coloured skin)
- 6. Cutaneous lesions in areas covered by tattoos
- 7. Cutaneous lesions in abundantly hairy skin areas (provided the the area cannot be shaved freely from the hair to allow clear view for the dermatoscope)
- 8. Images where the entire lesion is not inside the photo
- 9. Images that are out of focus

Methodology

The subjects will be included from around 30 primary care centres in Sweden. If the subject's lesion(s) is suspected of melanoma or melanoma cannot be ruled out, the subject is asked to participate in the investigation.

The investigator examines the subject's lesion(s) and makes the clinical assessment of the subject lesion(s) based on established clinical decision algorithms (such as "Chaos & clues", "3- or 7-point checklist", or the ABCDE concept) of whether there is a suspicion of MM, according to the usual clinical routine (also includes very low suspicion of MM but cannot be completely dismissed). The investigator takes dermoscopy images according to standard of care and archives the image(s) according to clinical routine. The investigator decides on action, based on his or her MM suspicion (excision at the primary care centre or referral for excision or referral to a dermatologist for further

Template Doc. id. Version

02

Document	Doc. id.	Version	Page	
Clinical investigation Plan / Investigation code- AI-DSMM/	GR 21- 023	01	11 (52)	_

assessment). If the subject has agreed to participate in the investigation, the investigator indicates in the CRF the clinical suspicion level of MM, and decided action.

The investigator takes images of the lesion(s) again, this time with a mobile phone, containing the IMD AI SW, connected to a dermatoscope, and follows the on-screen instructions. The image is processed by the AI SW and the results are visible on the screen within seconds. A unique auto generated code number is also presented. The code number is registered on the enrollment log and in the CRF. The investigator records how he considers that the degree of suspicion of MM (higher vs lower) would have been affected by the AI SW result if it had been the governing body for the treatment.

When the subject has been fully examined and receives the final tumor diagnosis from the histopathology/PAD results (melanoma/non melanoma), the degree of agreement between the PAD and the outcome of the AI SW decision support is calculated with the Kappa-analysis and the diagnostic accuracy to be able to distinguish melanoma from non-melanoma in the form of sensitivity and specificity as well the positive and predictive value. The corresponding comparison is performed from the examining investigators' estimated clinical degree of suspicion, as well as the diagnostic accuracy when both the PAD and the AI decision support are weighted together (i.e. in cases where the investigator and the decision support are in agreement in their assessment). The clinical investigation will collect information from the users, how participating users (investigators at the site) experience the usability of the AI SW decision support and attaching applications, from short surveys including the validated System Usability Scale.

Use the same overall description given in Section 9.1.

Duration of exposure to the Investigational Medical Device

The subjects will not be in any direct contact with IMD Dermalyzer.

Duration of subjects' involvement in the investigation

The subjects will only perform 1 visit at a primary care centre to assess the cutaneous lesion(s).

Clinical performance assessments

The subject will be examined according to clinical routine. The cutaneous lesions where MM cannot be ruled out (study lesions) will be photographed with a digital dermatoscope. The digital image will then be able to be instantly uploaded to the study's AI enhanced web application (Dermalyzer), where the AI algorithm performs the image analysis within a few seconds.

Template Doc. id. Version

02

CIP Template QMS 12-01-

Document	Doc. id.	Version	Page
Clinical investigation Plan / Investigation code- AI-DSMM/	GR 21- 023	01	12 (52)

Clinical safety assessments

All considered reportable events in accordance with MDR, will be captured. The subject included in the investigation will follow the standard of care. The use of the AI will not influence the subject or the medical care of the subject.

Statistical methods

The sample size of at least eligible 239 lesions is calculated by an expected true proportion of 95% with 80% power. The estimated frequency of actual found malignant melanoma is 4.65% (or 12 MM out of 239 lesions).

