7.1 Background

Malignant melanoma is a type of tumor resulting from an uncontrolled proliferation of melanocytes (pigment-producing cells), a type of cell found in the mucous membranes, eyes, and innermost layers of tissue covering the brain and spinal cord^{1,2}. Despite advances in both diagnosis and treatment of malignant melanoma, the disease is still a major challenge within healthcare¹. The incidence of the disease among several fair-skinned populations has increased with as much as 4-6 percent yearly^{1,3} and melanoma is one of the cancer types with the highest average years of life lost per death (15 years), so-called AYLL⁴. Melanoma accounts for only 5 percent of cutaneous malignancies, but can be attributed to most skin cancer deaths¹.

During 2020 it was estimated that Europe had a total incidence of approximately 150,000 and the total number of deaths caused by melanoma was approximately 26,000. North America had a total incidence of approximately 105,000 and the total number of deaths caused by melanoma was approximately 8,500. Oceania had a total incidence of approximately 19,000 and the total number of deaths caused by melanoma was approximately 2000⁵.

Document	Doc. id.	Version	Page	
Clinical investigation Plan / Investigation code- AI-DSMM/	GR 21- 023	01	20 (52)	

Primary care and general practitioners play a vital role in detecting patients with suspected skin lesions and thus in detecting melanoma at early stages⁶. Histopathology (or 'Pathologic anatomic diagnosis', PAD) is considered the gold standard in melanoma diagnosis. For histopathological diagnosis the suspected lesion is excised and inspected by a dermatopathologist, who can report on characteristics, such as melanoma subtype, tumor thickness and ulceration. If the malignancy is not detected at an early stage and is allowed to metastasize and spread outside its primary location, it is more challenging to treat and the chance of survival decreases¹. If detected at an early stage, excision of the skin lesion is associated with a high chance of survival⁷. On the other hand, unnecessary excision of benign skin lesions are common and leads to increased morbidity as well as increased healthcare costs⁸. The direct and indirect healthcare and societal costs for diagnosing and treating malignant melanoma, as well as costs associated to melanoma deaths, are significant ^{1,8}.

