9.4.10 Blinding

The Investigators will have to document their assessment of the included lesion(s) in the eCRF before taking the IMD image in order not to be influenced by the IMD result. When the outcome of the IMD AI result is available the Investigator will evaluate if his/her decision would have changed if taking the result of the AI into consideration.

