The set expectation of 95% true proportion is based on in-silico experiments on a proprietary dataset of images which found a sensitivity of 95.1 \pm 0.6%.

The accuracy of AI decision support will be measured against gold standard (PAD) as well as against experienced dermatologists and general practitioners (average) and verified at: sensitivity> 95%, specificity> 75%, numbers needed to excise (NNE) <7, positive predictive value (PPV))> 15% and negative predictive value (NPV)> 99.5%. The average sensitivity for general practitioners in previous meta-analyzes is estimated at about 81%.

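### The planned accuracy for investigator and AI combined covers only lesions on which the two agree, so it is conditional on agreement and does not estimate combined accuracy in all PAD-verified lesions

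*Combined protocol and SAP*

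**What the plan says.** The Methodology part of the synopsis plans kappa, sensitivity, specificity and predictive values for the AI against PAD. It plans the same comparison for the investigator's own level of suspicion, and then one further accuracy result for two sources combined: "both the PAD and the AI decision support are weighted together (i.e. in cases where the investigator and the decision support are in agreement".

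Taken literally, PAD is one of the two things being combined. Yet section 7.1 says PAD "is considered the gold standard in melanoma diagnosis", and section 9.7.6 says "The accuracy of AI decision support will be measured against gold standard (PAD". The parenthesis in the synopsis names the intended pair: the investigator and the decision support.

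Section 9.4.10 has the investigator's assessment recorded before the AI image is taken. Afterwards, "the Investigator will evaluate if his/her decision would have changed if taking the result of the AI into consideration".

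The combined analysis is not among the endpoints in section 8 and is not described in section 9.7. Section 9.7.3.2 refers further analyses to an SAP whose text is not in the document available for this review.

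**The concern.** The parenthesis makes agreement the definition of the combined result. Accuracy among agreeing lesions answers how often the two are right when they agree. Combined use raises a different question: how accurate is the pair over every lesion examined? Lesions on which the two differ are the ones where decision support can alter a judgement, and they are left out.

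At stake is what the trial can say about using the device alongside the clinician, which is its intended use. A high agreement-only figure could be taken for the performance of the pair. The primary endpoint does not share the problem: it concerns the AI alone and counts all four cells of Table 1 in section 9.7.6.

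**Working it through.** **The plan's own figure.** The plan gives no number for this analysis. Its sample size rests on "an expected true proportion of 95% with 80% power". With π0 = 90%, π1 = 95% and one-sided 2.5%, n = [(1.960·√(0.90·0.10) + 0.842·√(0.95·0.05))/0.05]² = 238.03, rounded up to 239. That reproduces, and the point below does not touch it.

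**Algebra.** Within melanomas, or within non-melanomas, let r = share both classify correctly, w = share both classify wrongly, and d = 1 − r − w = discordant share.

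- Agreement-only accuracy: a = r/(r + w).
- Either-positive rule, all lesions: sensitivity 1 − w, specificity r.
- Both-positive rule, all lesions: sensitivity r, specificity 1 − w.
- Any rule that keeps the shared call where the two agree must lie between r and 1 − w, since its result is r plus the part of d it gets right.
- Because a = r + a·d, reading a as all-lesion accuracy assumes that discordant lesions are resolved correctly as often as agreeing ones.

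**Inputs from the plan.** 12 melanomas of 239 lesions, so 227 non-melanomas (synopsis). AI sensitivity 95.1% (in-silico result, section 9.7.6). AI specificity 75%, from the verification limits "sensitivity> 95%, specificity> 75%, numbers needed to excise (NNE) <7". GP sensitivity: "The average sensitivity for general practitioners in previous meta-analyzes is estimated at about 81" percent.

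**Assumptions.** GP specificity 60–75%. AI specificity 95% as an alternative, because the planned overall proportion needs it: (12·0.951 + 227·0.75)/239 = 76.0%, whereas (12·0.951 + 227·0.95)/239 = 95.0%.

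**Independent errors.**

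- Melanomas: r = 0.81·0.951 = 0.7703; w = 0.19·0.049 = 0.0093; a = 0.9881; d = 0.2204, or 2.6 of 12.
- Non-melanomas, AI specificity 75%: GP 60% gives r = 0.45, w = 0.10, a = 0.818, d = 0.45 (102.2 of 227). GP 75% gives r = 0.5625, w = 0.0625, a = 0.900, d = 0.375 (85.1).

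**Maximal positive dependence** (r and w as large as the margins allow).

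- Melanomas: r = 0.81, w = 0.049, a = 0.943, d = 0.141 (1.7 of 12).
- Non-melanomas, AI specificity 75%: GP 60% gives a = 0.60/0.85 = 0.706; GP 75% gives a = 0.75 and d = 0.

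**Results** (sensitivity / specificity, %; ranges are over GP specificity 60–75%):

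| Error pattern, AI specificity | Agreement-only | Lesions omitted | Either-positive | Both-positive |
|---|---|---|---|---|
| Independent, 75% | 98.8 / 82–90 | 37–44% | 99.1 / 45–56 | 77.0 / 90–94 |
| Independent, 95% | 98.8 / 96.6–98.3 | 27–40% | 99.1 / 57–71 | 77.0 / 98.0–98.8 |
| Correlation 0.3, 75% (AI sensitivity rounded to 95%) | 95.8 / 76–84 | 26–32% | 96.5 / 51–62 | 79.5 / 84–88 |
| Maximal dependence, 75% | 94.3 / 71–75 | 1–15% | 95.1 / 60–75 | 81.0 / 75 |
| Maximal dependence, 95% | 94.3 / 92.3–93.8 | 20–34% | 95.1 / 60–75 | 81.0 / 95 |

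Under independence the agreement-only figure pairs a sensitivity close to the either-positive rule with a specificity that rule cannot reach.

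**Cut-off.** Exclusion criterion 1 (section 9.3.5) removes lesions the investigator considers benign. If any degree of suspicion counted as investigator-positive, every study lesion would be positive. Agreement would then simply mean AI High, and the agreement-only result would be sensitivity 100% and specificity 0%, whatever the device does.

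**The case against.** The restriction is disclosed in the same sentence, and nothing in the plan presents the figure as accuracy in all lesions. The analysis is peripheral: it appears only in the synopsis, is not an endpoint and carries no threshold of its own. Accuracy of the AI and of the investigator is planned separately. Section 9.7.1 promises line listings of all data, so discordant lesions could be recovered, and the question in section 9.4.10 is asked without restriction to agreeing lesions. All of this stands and limits the weight of the point.

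The size also rests on assumptions. GP specificity is not in the documents, and the 81% comes from meta-analyses, not from lesions already selected as suspicious. With maximal dependence and both specificities at 75%, agreement-only (94.3% / 75%) and either-positive (95.1% / 75%) differ by 0.8 points in sensitivity and not at all in specificity. With about 12 melanomas, sensitivity is imprecise anyway: the exact 95% interval is 73.5–100% for 12/12, 61.5–99.8% for 11/12 and 66.4–100% for 9/9.

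None of this makes agreement-only accuracy an estimate of combined accuracy. Line listings permit a later analysis but do not prespecify one.

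A reader might infer that the figure must flatter the combination. The documents do not support a fixed direction: under maximal dependence it is no better than the AI alone (94.3% against 95.1% sensitivity). A reader might also infer that PAD is really meant as an input, or that no rule for discordant lesions exists. The parenthesis contradicts the first. The second cannot be established without the SAP text.

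**Conclusion.** The point holds as a matter of definition. The figure described in the synopsis is accuracy conditional on agreement, and it leaves out every lesion on which exactly one assessor is wrong. How far it departs from an all-lesion result cannot be fixed from the documents: in the cases tried the specificity gap to the either-positive rule runs from none to over 30 points, and the share omitted from about 1% to 44%. These sizes depend on assumed GP specificity, assumed error dependence and a suspicion cut-off that the available text does not state (Figure 1 is not shown, and the SAP may define it).

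The consequence is limited to a supporting analysis; the primary test and N = 239 stand. It still merits correction, because as worded the sentence uses the reference standard as an input and cannot support a statement about combined use.

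**What to change.** 1. In the synopsis, replace PAD as an input with the investigator's assessment recorded before the AI image, and keep PAD only as the reference.
2. State, before PAD results are seen, which suspicion level counts as investigator-positive. Neither agreement nor any combined rule is defined without it.
3. Label the agreement-only figure as conditional on agreement, and give the number of melanomas and non-melanomas it excludes.
4. Tabulate investigator by AI by PAD for all PAD-verified lesions, including discordant ones.
5. Report sensitivity and specificity with exact confidence intervals under the either-positive and both-positive rules. Present them as descriptive bounds on combined use, not as rules for practice, and note the imprecision from about 12 melanomas.

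Cost: one wording correction, a matching SAP definition if it lacks one, and a few tables from data already collected. No extra lesions or visits are needed. The drawback for the sponsor is that an all-lesion combined result may look less favourable.

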4 LIST OF ABBREVIATIONS AND DEFINITION OF TERMS

Abbreviation or term	Explanation	
AE	Adverse Event	
ADE	Adverse Device Effect	
Al	Artificial Intelligence	
AIMT	AI Medical Technology AIM AB	
ASADE	Anticipated Serious Adverse Device Effect	
CIP	Clinical Investigational Plan	
CRF	Case Report Form	
DD	Device Deficiency	
EEA	European Economic Area	
FAS	Full Analysis Set	
ICF	Informed Consent Form	
Template	Doc. id.	١

CIP Template QMS 12-01- 02 01

Document	Doc. id.	Version	Page	
Clinical investigation Plan / Investigation code- AI-DSMM/	GR 21- 023	01	13 (52)	

IEC Independent Ethics Committee

IFU Instructions for use

GCP Good Clinical Practice

IMD Investigational Medical Device

MM Malignant Melanoma

MDSW Medical Device Software

N/A Not applicable

PAD Pathological Anatomical Diagnosis

SAE Serious Adverse Event

SADE Serious Adverse Device Effect

SD Standard Deviation

SOP Standard Operating Procedure

TMF Trial Master File

USADE Unanticipated Serious Adverse Device Effect

Enrolled subject Subject who has signed the Informed Consent Form (ICF)

Screen failure Enrolled subject not included

Included subject Subject fulfilling the eligibility criteria

Withdrawn subject Subject included but not completed

Document	Doc. id.	Version	Page
Clinical investigation Plan / Investigation code- AI-DSMM/	GR 21- 023	01	14 (52)

Completed subject

Subject completed the investigational period, including follow-up

5 ETHICAL AND REGULATORY REQUIREMENTS

5.1 Ethical and regulatory review

Necessary approvals of the Clinical Investigational Plan (CIP), the subject Information sheet and Informed Consent Form (ICF) must be obtained before enrolment of any subject into the investigation. The written approvals, including an identification of the investigation and the date of review, will be filed in the Sponsor File and at the Investigation Site File.

It is the responsibility of the Sponsor to keep the IEC and Competent Authority informed of Serious Adverse Events (SAEs) or device deficiencies that could have led to a SAE, any substantial amendments to the CIP and any safety updates/reports during the investigational period, according to local requirements.

All correspondence with the IEC and Competent Authority will be filed both in the Sponsor Trial Master File (TMF).

5.2 Ethical conduct of the investigation

The investigation will be performed in accordance with the recommendations guiding physicians in biomedical research involving human subjects that were adopted in 1964 by the 18th World Medical Assembly, in Helsinki, Finland, with later revisions and ISO 14155:2020.

The Declaration of Helsinki is included as Appendix 13.2 to the CIP.

5.3 Subject information and consent

It is the responsibility of the Investigator to give each potential investigational subject, adequate verbal and written information regarding the objectives and the procedures of the investigation as well as any risks or inconvenience involved before including the subject. The subject must be informed about the right to withdraw from the investigation at any time. The subject should be allowed sufficient time for consideration of the proposal.

Furthermore, it is the responsibility of the Investigator to obtain signed informed consent from all subjects before including them in the investigation. The ICF must be signed and personally dated by

Document	Doc. id.	Version	Page
Clinical investigation Plan / Investigation code- AI-DSMM/	GR 21- 023	01	15 (52)

the subject and by the Investigator before any investigation-specific procedures are performed, including screening procedures. A copy of the Subject Information and the signed ICF will be provided to the subject.

Documentation of the discussion and the date of informed consent must be recorded in the source documentation and in the Case Report Form (CRF). The signed Subject Information sheet and ICF should be filed by the Investigator for possible future audits and/or inspections.

The final version of the Subject Information sheet and ICF are submitted to the IEC and concerned Competent Authority and must not be changed without permission from Sponsor, the Competent Authority and the local IEC.

The subjects will be asked for participation in the clinical investigation when seeking care for suspicious cutaneous lesions at the primary care centre. The subject can also be identified if an investigator sees a suspicious lesion when examining the subject for another purpose. If the subject's lesion(s) is suspected of MM or MM cannot be ruled out the subject is asked to participate in the investigation. The subject receives oral and written study information and will have time to read the information and ask any questions. If the subject voluntarily agrees to participate the consent form is signed before any investigation assessments are collected.

